7.5 Definitions of Response –

7.5.1 Primary Endpoint - PSA doubling-time response

- 7.5.1.1 Definition: a 50% increase in the PSADT compared to pre-enrollment PSADT.
- 7.5.1.2 PSADT will be calculated based on the MSKCC calculator, available at http://www.mskcc.org/mskcc/html/10088.cfm.
- 7.5.1.3 PSADT response will be measured at 9 and 18 months after initiation of the research intervention.
- 7.5.1.4 Three measurements of PSA, spaced at least 2 weeks apart, will be required prior to study enrollment. Post-intervention PSADT will be based on PSA levels at 3, 6 and 9 months (9 month PSADT calculation) and 3, 6, 9,12,15,18 month levels (18 month PSADT calculation).

7.5.2 Secondary Endpoint – PSA response

7.5.2.1 Definition: a 50% reduction in the pre-research intervention PSA value, verified with a second measurement >28 days later.

7.5.3 Progression:

Progression of disease is defined for 3 different categories of disease: measurable lesions; non-measurable/non-target lesions; and PSA-only disease. The first category of disease to progress will meet the definition of progression in this trial, as follows:

7.5.3.1 Progression for measurable disease:

Definition: Measurable lesions are defined as those that can be accurately measured in at least one dimension (longest diameter to be recorded) and is equal or greater than 20 mm with conventional techniques (CT, MRI, x-ray) or equal or greater than 10 mm with spiral CT scan. All tumor measurements must be recorded in millimeters (or decimal fractions of centimeters)

All measurable lesions (up to a maximum of 10) representative of all involved organs should be identified as target lesions and will be recorded and measured at baseline. Target lesions should be selected on the basis of their size (lesions with the longest diameter) and their suitability for accurate repetitive measurements (either by imaging techniques or clinically). A sum of the longest diameter (LD) for all target lesions will be calculated and reported as the baseline sum LD. The baseline sum LD will be used as reference to further characterize the objective tumor response of the measurable dimension of the disease.

All other lesions, including non-measurable small lesions as defined above and bone metastasis, will be identified as non-target lesions (see definition of progression for non-target lesions below).

Progression is defined if any of the criteria below are met:

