- at least a 20% increase in the sum of the LDs of target lesions (taking as a reference the smallest sum LD recorded since the treatment started) or the appearance of two or more new lesions
- development of an indication for radiation therapy while on treatment
- 7.5.3.2 Progression for non-measurable disease/non-target lesions:

Non-measurable disease/non-target lesions: progression of disease is defined as any of the following:

- 7.5.3.2.1 worsening bone scan as evidenced by the appearance of more than two new lesions, not felt to be consistent with a tumor flare; worsening of pre-existing lesions (increase in intensity or size of a lesion) may be difficult to interpret and in such a case will not be considered the evidence of progressive disease; or
- 7.5.3.2.2 appearance of new metastatic lesions outside the bone; or unequivocal progression of existing non-target lesions. Because a clear progression

- of non-target lesions only is exceptional, such circumstances should be discussed with the study co-investigator's; or
- 7.5.3.2.3 development of an indication for radiation therapy while on treatment
- 7.5.3.3 Progression for patients with PSA-only disease

PSA progression will be evaluated as follows:

- 7.5.3.3.1 In patients that had any PSA decline from baseline:
 - 7.5.3.3.1.1 increasing PSA by 25% above the nadir plus
 - 7.5.3.3.1.2 an increase in PSA by a minimum of 2 ng/ml from the nadir plus
 - 7.5.3.3.1.3 confirmation by second consecutive rising PSA >28 days later
- 7.5.3.3.2 in patients whose PSA has not declined, progression is defined as
 - 7.5.3.3.2.1 an increase in PSA by 25% above the pretreatment level plus
 - 7.5.3.3.2.2 an increasing PSA by a minimum of 2 ng/ml relative to the study entry PSA value, plus
 - 7.5.3.3.2.3 confirmation by second consecutive rising PSA >28 days later.
- 7.5.4 Onset of Response In patients that present with radiologic evidence of metastases onset of response is the onset of PR or CR. For patients with biochemical disease only the onset of response is defined by the first drop in serum PSA.

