- 7.5.5 Duration of Response In patients that present with radiologic evidence of metastases, duration of response is time from onset of PR or CR, whichever occurs first, (even if the patient later has a CR) until objective evidence of progression. In patients with PSA-only disease, duration of response is time from first drop in serum to objective evidence of progression. Progression is defined in Section 7.5.3, beginning on page 20.
- 7.6 Timing of Toxicity Assessments Toxicity assessment will occur as stated in the calendar.

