	Std. of Care or Res.	Prior to Reg. ¹	Day 1 First Inj.	30 d. 2 nd Inj.	44 d.	60 d. 3 rd Inj.	74 d.	90 d.	6 mo	9 mo	12 mo	18 mo.	24 mo.	Annual to prog.	Follow- up ⁷
Immunization ²	R		X	X		X									
Physical Examination	S		X	X		X		X							
Adverse Event Assessments	R		X	X		X		X							
Performance Status	S		Х	Х		X		X	X	X	Х				
Vital Signs	S		X	X		X		Χ	X	X	Х				
Weight	S		Х	Х		X		Χ	Х	Х	Х				
Blood for PSA & PAP ³	S/R		Х	X (R)		X(R)		Χ	Х	Х	Х	Х	Х		
anti-PSA Ab, and lymphocytes for cellular immunity	R	Х	Х	Х	Х	Х	Х	Х	X _e	X ⁶	X ₆	Х	Х		
CBC, differential	R	Х		Х		X		Х	Х	Х	Х	Х	Х		
AST, ALT, LDH, alkaline phosphatase, bilirubin	R	Х		Х		Х		Х							
Creatinine	R	Х		Х		X		Х							
Urinalysis	R	Х		Х		X		Х							
Serum testosterone	R	Х													
Chest x-ray	R	Х		X ⁴		X ⁴		X ⁴							
Bone scan	S	Х						Х	Х		Х		Х	Х	
Abdominal/pelvic CT	S	Х							X ⁵		X ⁵				
Survival assessment	R														X ⁷

S = Procedures considered "Standard of Care" for prostate cancer patients.

R = Procedures considered "Research" as part of this Clinical Trial.

In the event of holidays or other extenuating circumstances the times on the table may vary by ± 4 days for the first 90 days. Beyond that every effort will be made to see the patient within 2 weeks of the expected date of return, but the investigator is willing to allow for other arrangements for the convenience of the patient.

¹ Reg. = Registration, the date patient eligibility approved by the study team.

² Androgen deprivation therapy must continue for the duration of study participation.

³ If the PSA meets the definition of progression, partial or complete response, confirm the PSA results >/= 28 days.

⁴ will be repeated only if abnormal at screening or if patient develops a fever.

⁵ will be repeated only if abnormal at screening.

⁶ to be performed even if there is disease progression (up to 12 months from study entry) if the patient has consented to this in the informed consent (question in section "How long will I be on the study?)."

⁷ Follow-up for survival every 6 months by telephone.

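### For PSA-only men, onset and duration of response start at any first PSA fall, which conflicts with the confirmed 50% reduction that defines PSA response

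*Combined protocol and SAP*

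**What the plan says.** Section 7.5 of the combined protocol and SAP gathers the response definitions under one heading.

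- **PSADT response (7.5.1.1, primary):** "Definition: a 50% increase in the PSADT compared to pre-enrollment PSADT". No fall in PSA is needed.
- **PSA response (7.5.2.1, secondary):** "a 50% reduction in the pre-research intervention PSA value, verified with a second measurement >28 days later".
- **Onset, men with radiologic metastases (7.5.4):** "In patients that present with radiologic evidence of metastases onset of response is the onset of PR or CR".
- **Onset, PSA-only men (7.5.4):** "For patients with biochemical disease only the onset of response is defined by the first drop in serum PSA".
- **Duration, PSA-only men (7.5.5):** "In patients with PSA-only disease, duration of response is time from first drop in serum to objective evidence of progression".

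Two other places bear on the point. Section 7.5.3.3.1 opens its progression rule with "In patients that had any PSA decline from baseline" and uses such a decline only to choose the nadir as the reference for progression. Footnote 3 to Table 6 asks for confirmation of PSA results: "If the PSA meets the definition of progression, partial or complete response, confirm the PSA results >/= 28 days".

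Scan-negative men are eligible under 3.1.2 whatever their PSADT, so the PSA-only rule has patients to apply to.

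**The concern.** Within one section the word response carries two meanings for the same men. In 7.5.2.1 it is a large, confirmed fall. In 7.5.4 and 7.5.5 it begins with a fall of any size, seen once, against a reference that is not named (day 1 or the previous visit).

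PSA varies from one measurement to the next. A man whose PSA is truly rising can have one value slightly below an earlier one. Taken literally, that value is an onset of response, and the time to progression from there is a duration of response, although he never met the definition of response. In a single-arm trial there is no control group to show how often this happens by chance. At stake is whether a reported response duration measures the response that the protocol defines.

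**Working it through.** **1. The texts side by side.** There is no stated figure to reproduce, because the point rests on definitions.

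| Element | 7.5.2.1 (PSA response) | 7.5.4 and 7.5.5 (PSA-only men) |
|---|---|---|
| Size of fall | 50% | none given |
| Reference value | pre-intervention PSA | none given |
| Confirmation | more than 28 days later | none given |
| Restricted to responders | defines them | not stated |

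For men with radiologic metastases, 7.5.4 and 7.5.5 start at PR or CR, which is a response category. Only the PSA-only branch is detached from one. Section 7.5.3.3.1 also shows that the protocol can treat a mere decline as something other than a response.

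**2. Two readings.**

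- *Literal:* any PSA-only man with a fall gets an onset, and a duration once he progresses.
- *Responders only:* the man later meets 7.5.2.1, but his clock is back-dated to the first fall. As an invented example at Table 6 visit times, suppose PSA dips slightly at day 30 and first reaches half the pre-intervention value at month 6, later confirmed. Onset is then month 1 instead of month 6, and duration is 6 − 1 = 5 months longer.

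**3. How often noise alone produces a fall.** The inputs from the documents are the Table 6 PSA times: day 1, days 30, 60 and 90 (taken as months 1, 2 and 3), and months 6, 9 and 12. The assumptions, which the documents do not give, are no vaccine effect, constant exponential growth with doubling time T, and independent normal errors on the log scale with SD σ from 0.05 to 0.20.

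At one visit at month t:

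P(PSA below day 1) = Φ(−(ln 2 · t/T) / (σ√2))

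For T = 12 months, σ = 0.10 and t = 1, ln 2/12 = 0.0578 and σ√2 = 0.1414. The ratio is 0.41 and the probability is about 0.34. For a value at or below half of day 1, the numerator becomes 0.693 + 0.058 = 0.751, the ratio is 5.3, and the probability is below one in ten million.

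Simulating 200,000 men per setting over all visits to month 12 gives:

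| PSADT | Share with any PSA below day 1 (σ 0.05 to 0.20) |
|---|---|
| 2 months | about 0–11% |
| 3 months | about 0–23% |
| 6 months | about 5–44% |
| 12 months | about 23–60% |
| 24 months | about 44–71% |

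In the same settings, a single 50% fall occurs in at most about 1.2–1.3% of men, and two consecutive ones in under 0.1%. If the fall is judged against the previous visit, which the text permits, the shares are 15–88%, 57–98% and 88–99.7% at PSADT 6, 12 and 24 months.

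**4. Check with follow-up stopped at PSA progression.** This run has visits to 24 months, 100,000 men per setting, an assumed within-man CV of 5–15% and an assumed baseline PSA of 5 or 20 ng/ml. It applies a simplified form of the 7.5.3.3 rule. The share with a value below baseline before progression is 0–14% at PSADT 3 months, 5–36% at 6, 23–54% at 12 and 44–67% at 24. Among those who then progress, the median time from that value to progression is about 1 month at PSADT 3, 2–5 months at 6, 5–6 months at 12 and 7–11 months at 24. A confirmed 50% reduction occurs in at most about 0.001%.

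**The case against.** The strongest reply is that onset of response presupposes a response. Sections 7.5.1 and 7.5.2 define response, and 7.5.4 and 7.5.5 only date it, so no sentence says that non-responders receive a duration. The text allows this reading and does not settle the matter. On it, the noise percentages do not apply, but the back-dating remains and so does the missing reference value.

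Second, duration of response may never be analysed. It is not among the objectives in Section 2, and Section 10 does not mention it. This stands, and it limits the weight of the point. A reader might infer from the definitions that the protocol plans to report durations, but no section says so.

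Third, a reader might infer that the rule overstates vaccine activity. The documents and the calculation do not show that. Back-dating lengthens duration in true responders, but men who enter through noise often have short durations (a median of about 1 month at PSADT 3 months), and adding them could lower a reported median. The response rate is still governed by 7.5.2.

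Fourth, the frequency depends on an assumed mix of doubling times. PSA-only men may have any PSADT. The 6-month minimum in 3.1.2 applies to scan-positive men, to whom this rule does not apply. In fast risers the effect is small.

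**Conclusion.** The conflict is on the face of the text and holds on either reading. Literally, PSA-only men without a PSA response can be given an onset and a duration. On the responders-only reading, the clock starts before the response criterion is met.

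The size depends on assumed PSADT and measurement SD, and the percentages are illustrative. A noise-only onset ranges from almost none to about a quarter of men at PSADT 2–3 months, and from about 5% to 71% at 6–24 months.

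The reach is narrow: one descriptive secondary measure, in the PSA-only part of a 31- or 32-man trial (the protocol gives both totals). The primary PSADT endpoint, PSA response rate, time to progression, sample size and toxicity stopping rules do not use 7.5.4 or 7.5.5 and are unaffected. The net direction of bias in reported duration is not established.

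**What to change.** Change two sentences, using the protocol's own threshold:

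- **7.5.4:** for PSA-only men, onset is the date of the first PSA at least 50% below the pre-intervention value that is later confirmed under 7.5.2.1.
- **7.5.5:** for PSA-only men, duration runs from that date to progression as defined in 7.5.3, and is computed only in men who meet 7.5.2.

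Add that this is the duration of PSA response and not of PSADT response. A man with a PSADT response may never have a PSA fall, so he has no onset date under either wording. Reconcile Table 6 footnote 3 at the same time, since it allows confirmation at exactly 28 days where 7.5.2.1 requires more than 28.

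No visit, sample or patient number changes. The cost is fewer reportable durations, possibly none: Section 1.4 records no sustained fall in individual PSA levels in the Phase I trial.

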8 STUDY PARAMETERS

- 8.1 Scans or x-rays used to document measurable or evaluable disease must be done with 6 weeks prior to the initiation of treatment.
- 8.2 CBC with differential, LFT's must be done ≤2 weeks before study entry. Castrate levels of testosterone must be drawn at initiation of treatment.
- 8.3 All chemistries must be done <2 weeks before the study entry, unless specifically required on day 1 as per protocol. If abnormal, they can be repeated within 48 hours prior to the initiation of treatment.
- 8.4 Hgb, Hct, WBC, Plt must be done <2 weeks before study entry but, if abnormal, they can be repeated <48 hours prior to initiation of treatment.
- 8.5 REMOVAL OF PATIENTS FROM STUDY (Criteria for discontinuation of a patient's study participation)
 - 8.5.1 Adverse events: Study subjects will be monitored for adverse events for 30 days beyond the final study injection, or longer if existing unresolved AEs are being monitored. In the event of a vaccine-associated unmanageable or irreversible toxicity, that would include hematological and non-hematological toxicities, the investigator will withdraw a patient from further research intervention and notify the Study Chair immediately. In addition, the FDA and the IRB and other agencies listed on page 17 will be notified of the adverse events. If unmanageable or irreversible toxicities occur the patients will receive the best possible medical care according to the recommendations of the treating physicians. The treatment plan will depend upon what unmanageable or irreversible toxicities may occur. In the event of an emergency the patient will be instructed to seek immediate care by calling 911, his local physician, the University of Iowa or Iowa City VA Health Care System urology staff on call.

8.5.1.1 Management of Toxicities

8.5.1.1.1 Hematological Toxicity Management

- 8.5.1.1.1.1 Patients with grade 2 or 3 hematological toxicity will not receive the subsequent dose of vaccine until there is normalization of cbc parameters until grade 1 or less toxicity is reached. An exception to withholding a dose of vaccine would be if the cbc parameters were stable (at or near the pre-vaccination values).
- 8.5.1.1.1.2 In case of grade 2 or 3 hematological toxicity detected any time during protocol therapy, CBC with differential will be checked on a weekly basis until grade 1 or less toxicity is reached.
- 8.5.1.1.1.3 If the subsequent vaccine dose needs to be postponed for more than 2 weeks, those patients will be removed from protocol therapy.

- 8.5.1.1.1.4 Patients with grade 4 hematological toxicity at any time will be permanently removed from protocol therapy.
- 8.5.1.1.2 Non-Hematological Toxicity Management
 - 8.5.1.1.2.1 Patients with grade 2 or 3 non-hematological toxicity will not have the subsequent dose of vaccine administered until the toxicity ameliorates down to a grade 1 level.
 - 8.5.1.1.2.2 Patients will be evaluated once a week with study team assessments, if a grade 3 non-hematological toxicity occurs.
 - 8.5.1.1.2.3 If the subsequent dose of vaccine needs to be postponed for more than 2 weeks, those patients will be permanently removed from protocol therapy.
 - 8.5.1.1.2.4 Patients with grade 4 non-hematological toxicity at any time will be permanently removed from protocol therapy.

Patients may also be removed from protocol therapy at any time based on assessment of any other risks, at the discretion of the study investigators.

- 8.5.2 Disease Progression: Patients will be taken off-study if they have progressive disease (PD) or clinically significant deterioration at any time during the study if the investigator feels that (a) alternative prostate cancer therapy might benefit the patient, or (b) to continue on study might be unsafe for the patient. Patients receiving alternative prostate cancer therapies will be followed for toxicity for 30 days beyond the third AdPSA injection only unless existing unresolved AEs are being monitored. Patients will be asked in the Informed Consent document whether they would return every three months up to 12 months from study entry for immunologic evaluations. Patients who are being treated with prednisone at doses higher than 10 mg daily (or equipotent steroid doses) will be excluded from these every three month returns.
- 8.5.3 Allergic Reactions: Patients must be removed from the study should they develop grade II allergic reactions.
- 8.5.4 Personal Reasons: As stated in the informed consent, patients may withdraw from the study at any time.
- 8.5.5 Clinical Judgment: A patient may be withdrawn from the study, if, in the opinion of the investigators, it is not in the patient's best interest to continue (e.g. an adverse experience, intercurrent illness, non-compliance, etc.)
- 8.5.6 The date of discontinuation and the reason(s) for patient discontinuation from the study will be recorded in the CRF. All efforts will be made to conduct evaluations that are required at the follow-up for each patient who discontinues research intervention, regardless of the reason.

Regulatory and Reporting Requirements

The Data and Safety Monitoring Committee (DSMC) of the Holden Comprehensive Cancer Center will provide data and safety monitoring for this study. "The Data and Safety Monitoring Plan of the Holden Comprehensive Cancer Center" provides standard operating procedures to monitor all clinical cancer trials at the UIHC. All investigator-initiated trials are automatically monitored by the DSMC. A detailed data and safety monitoring plan for this study is on file with the DSMC and the Clinical Research Safety Officer (CRSO).

Data Management, Quality Control and Data Security

In order to protect confidentiality the subject will be assigned an identification number. This number will be used on all specimens from the subject and will be used for documentation purposes.

Data management for the optimal entry, processing, storage, and retrieval for this protocol's data will be accomplished by the principal investigator. The database will be located on a computer or in a locked cabinet in a locked office. This computer will be secured, accessible only by the research team. There will be more than one copy of the database. The second, secured, copy of the protocol data will be stored in a locked room accessible only by the research team. For quality control, auditing, and checking data for integrity, there will be a regular accounting of data periodically performed. The medical record and research record will be linked by the study identification number. The data managers in this trial will be responsible for verification of the accuracy of all data transferred from the medical record to the research record. These records will be audited quarterly by the Data Safety Monitoring Committee. All Data Safety Monitoring Committee reports will be provided to the USAMRMC Office of Research Protections, Human Research Protection Office as they become available.

Data will be kept on file on each patient for at least two years past the termination of that patient's participation in the trial. All records will be stored long-term in a secure location. UIHC records will be kept for at least 15 years and then confidentially destroyed. VAHCS records will be retained until disposition instructions are approved by National Archives and Records Administration.

Information from the medical records of patients referred by physicians outside the University of lowa and the VA Health Care System required to determine eligibility for this protocol will be placed in a research folder, identified by the patient code and will be available only to members of the clinical trial team (identified on pages 30 and 31). The signed HIPAA forms will be kept in the patient's folder in the office of the referring physician. The records of such patients that are deemed ineligible following a screening procedure will have their signed Release of Information forms, informed consent document, and eligibility form kept in a research folder under similar security conditions. The records for ineligible subjects will be stored with the other research records as indicated above.

Table 6
Study Design and Testing

	Std. of Care or Res.	Prior to Reg. ¹	Day 1 First Inj.	30 d. 2 nd Inj.	44 d.	60 d. 3 rd Inj.	74 d.	90 d.	6 mo	9 mo	12 mo	18 mo.	24 mo.	Annual to prog.	Follow- up ⁷
Immunization ²	R		X	X		X									
Physical Examination	S		X	X		X		X							
Adverse Event Assessments	R		X	X		X		X							
Performance Status	S		Х	Х		X		X	X	X	Х				
Vital Signs	S		X	X		X		Χ	X	X	Х				
Weight	S		Х	Х		X		Χ	Х	Х	Х				
Blood for PSA & PAP ³	S/R		Х	X (R)		X(R)		Χ	Х	Х	Х	Х	Х		
anti-PSA Ab, and lymphocytes for cellular immunity	R	Х	Х	Х	Х	Х	Х	Х	X _e	X ⁶	X ₆	Х	Х		
CBC, differential	R	Х		Х		X		Х	Х	Х	Х	Х	Х		
AST, ALT, LDH, alkaline phosphatase, bilirubin	R	Х		Х		Х		Х							
Creatinine	R	Х		Х		X		Х							
Urinalysis	R	Х		Х		X		Х							
Serum testosterone	R	Х													
Chest x-ray	R	Х		X ⁴		X ⁴		X ⁴							
Bone scan	S	Х						Х	Х		Х		Х	Х	
Abdominal/pelvic CT	S	Х							X ⁵		X ⁵				
Survival assessment	R														X ⁷

S = Procedures considered "Standard of Care" for prostate cancer patients.

R = Procedures considered "Research" as part of this Clinical Trial.

In the event of holidays or other extenuating circumstances the times on the table may vary by ± 4 days for the first 90 days. Beyond that every effort will be made to see the patient within 2 weeks of the expected date of return, but the investigator is willing to allow for other arrangements for the convenience of the patient.

¹ Reg. = Registration, the date patient eligibility approved by the study team.

² Androgen deprivation therapy must continue for the duration of study participation.

³ If the PSA meets the definition of progression, partial or complete response, confirm the PSA results >/= 28 days.

⁴ will be repeated only if abnormal at screening or if patient develops a fever.

⁵ will be repeated only if abnormal at screening.

⁶ to be performed even if there is disease progression (up to 12 months from study entry) if the patient has consented to this in the informed consent (question in section "How long will I be on the study?)."

⁷ Follow-up for survival every 6 months by telephone.

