7 MEASUREMENT OF CLINICAL AND IMMUNOLOGICAL EFFICACY

7.1 Methods of Malignant Disease Evaluation - Each patient will have a baseline evaluation prior to the injection of the Ad/PSA vaccine. The measurements will include physical exam, temperature, weight, serum PSA, blood chemistries, urinalysis, a quantitative bone scan for bone metastases, chest x-ray, and CT for soft tissue metastases, and performance status for quality of life.

Patients will be seen in the Urology and Oncology Clinics (see Table 6 for schedule). The injection site will be examined for evidence of erythema, induration and necrosis and patients will have their temperature and weight recorded and the patients will be interviewed to determine whether they experienced any adverse reactions. Blood samples will also be taken for standard laboratory testing and measurement of PSA and anti-PSA immune responses (see Table 6). Patients recruited from the DMMCC will return to that facility for their follow-up examinations and laboratory testing on days 44, 74, and at 6, 9, 12 months and all subsequent visits. At the 6 month, 9 month, 12 month, and subsequent semi-annual visits each patient will be evaluated comparing the baseline visit measurements to those obtained at the specific visit.

Because changes to the clinical status of the patients will be prolonged, continued follow up will be important. Therefore, patients will return to the clinic for two additional visits, at 18 and 24 months, unless travel distance is a prohibitive factor. Follow-up of patients for survival will occur every 6 months by telephone.

- 7.2 Scans Bone scans will be performed at 90 days, 6 months, and 12 months during the first year as well as the 24 month visit and annually until progression. If there is measurable disease by CT scan at registration then CT scans will also be performed using the same schedule as the bone scans.
- 7.3 Use of Serum PSA for Disease Evaluation Based upon our pre-clinical experiments and the results from the Phase I clinical trial we expect the immunized men to produce anti-PSA antibodies. The levels of antibody will be measured by a flow cytometry assay as described by Cavacini, et al. used in our Phase I clinical trial (40). We will also explore the use of a second serum marker for prostate cancer, hK2 in collaboration with [name], [name], and [name] at the Mayo Clinic. Investigators at Mayo, along

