9.7 Injection Procedures & Observation

At the weekly meetings of the clinical trial team at which the eligibility of the patients is decided, orders for the initial vaccine injection will be written by clinician members of the team. Orders for the second and third vaccine injections will be written at the meetings as close to the date of the scheduled injections as possible. On the designated days of injections and immediately prior to vaccination, the Investigational Pharmacist will mix the Ad/PSA (10⁸ pfu or 4.4 x 10⁹ particles) with the Gelfoam powder (30 mg/ml). Each vial of the vaccine contains twice the volume needed for each injection. One half of the vial will contain the proper pfu and particles required for the vaccination. The injection material will be taken from the pharmacy in a 1 ml. syringe with 25 gauge needle and presented to staff in the Clinical Research Unit. Each patient will be injected with approximately 0.16 ml. of the vaccine/Gelfoam material subcutaneously in the thigh. The exact volume of the vaccination mixture (Ad/PSA in Gelfoam) is not as important as the exact number of pfu or particles and that is controlled by using the required volume from the dose vial. The empty syringe will be disposed of in a biohazard container.

Patients will remain in the CRU for two hours after each injection to be monitored for signs of adverse events.

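### Table 6 schedules no safety checks at the existing Day 44 and Day 74 visits, which does not sit with section 7.1 and leaves about 30 days after each dose without a scheduled toxicity test

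*Combined protocol and SAP*

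**What the plan says.** Injections are given on Days 1, 30 and 60 (section 5.1), each followed by two hours of observation (sections 5.1 and 9.7).

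Table 6 marks "Adverse Event Assessments" and physical examination at Days 1, 30, 60 and 90. The "CBC, differential" row is marked before registration, at Days 30, 60 and 90, and at later visits. The "AST, ALT, LDH, alkaline phosphatase, bilirubin" row, creatinine and urinalysis are marked before registration and at Days 30, 60 and 90. At Days 44 and 74 the only marked row is "anti-PSA Ab, and lymphocytes for cellular immunity".

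Section 7.1 gives a general description of clinic visits on the Table 6 schedule. The injection site is examined, temperature and weight are recorded, standard laboratory blood is taken, and "the patients will be interviewed to determine whether they experienced any adverse reactions". It adds that patients recruited from the Des Moines center "will return to that facility for their follow-up examinations and laboratory testing on days 44, 74", and at later visits. Section 7.6 says that toxicity assessment follows the calendar.

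The rules that use these data are in two places. Section 8.5.1.1 holds the next dose for grade 2 or 3 toxicity until it is grade 1 or less, removes patients with grade 4 toxicity at any time, and states: "In case of grade 2 or 3 hematological toxicity detected any time during protocol therapy, CBC with differential will be checked on a weekly basis". Section 10 stops the trial at 5 of 17 or 7 of 25 patients with grade 3 or higher toxicity, or at 2 of 17 with grade 4 or higher. On order timing, section 9.7 says: "Orders for the second and third vaccine injections will be written at the meetings as close to the date of the scheduled injections as possible".

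**The concern.** Under section 10, early termination rests on toxicity alone, so the visit schedule supplies the data for the trial's only early-stopping mechanism. Section 7.3 explains the laboratory frequency by the need to assess possible vaccination toxicity. The human experience described in section 1.4 is with a single injection; for three injections, section 10 cites only pre-clinical studies.

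Against that background, two visits bring men in and draw blood 14 days after doses 2 and 3, yet have no safety item in the calendar. A site reading section 7.1 could examine and test on those days, while a site reading Table 6 would not. Patients from the outside center could then be assessed differently from the others. Several rules apply to toxicity occurring or detected at any time, but no scheduled safety laboratory test falls between one injection day and the next.

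**Working it through.** **Step 1: the calendar.** Inputs are the injection days in section 5.1 and the marks in Table 6.

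| Dose | Day given | Existing visit between | Safety marks there | Next scheduled safety check | Gap |
|---|---|---|---|---|---|
| 1 | 1 | none | not applicable | Day 30, day of dose 2 | 30 − 1 = 29 days |
| 2 | 30 | Day 44 (44 − 30 = 14 days) | none | Day 60, day of dose 3 | 60 − 30 = 30 days |
| 3 | 60 | Day 74 (74 − 60 = 14 days) | none | Day 90, no injection | 90 − 60 = 30 days |

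**Step 2: section 7.1 against Table 6.** The general visit description in 7.1 refers to Table 6 for timing, so by itself it does not place an examination on Days 44 or 74. The sentence on outside-center patients does name those days and mentions both examinations and laboratory testing. Table 6 has no physical examination, vital signs, weight, adverse event or toxicity laboratory mark on either day. Because 7.6 defers to the calendar, the text leaves unclear which applies.

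**Step 3: which rules are exposed.**
- Dose hold: it depends on toxicity not yet back to grade 1. A grade 2 or 3 toxicity that has resolved by the next injection would not hold that dose even if it had been seen.
- Weekly CBC: it starts on detection, so it can be missed.
- Removal for grade 4 at any time: it can be missed if the event is laboratory-only and short.
- Stopping counts (5/17, 7/25, and 2/17 for grade 4): they can be under-counted for the same reason.

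**Step 4: what the stopping rule assumes.** Inputs from section 10: acceptable rate 15%, unacceptable rate 35%, looks at 17 and 25 patients.

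Formulas, with X binomial at rate p:
- Look 1: P(X₁₇ ≥ 5).
- Look 2 alone: P(X₂₅ ≥ 7).
- Either look: P(X₁₇ ≥ 5) + Σₓ₌₀..₄ P(X₁₇ = x) · P(X₈ ≥ 7 − x).

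At p = 0.35, look 1 gives 0.765 (plan: 77%) and look 2 gives 0.827 (plan: 82%). Either look gives 0.765 + 0.099 = 0.864. The stated power is therefore reproduced closely, and it takes every grade 3 or higher toxicity as captured. (The stated alphas of 0.05 are not reproduced: exact values are 0.099 and 0.070. That is a separate matter.)

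**Step 5: sensitivity to incomplete capture.** Let s be the share of patients with grade 3 or higher toxicity who are recorded. The documents give no value, so s is purely an assumption. The observed rate is 0.35 × s.

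| s (assumed) | Observed rate | Look 1 | Look 2 alone | Either look |
|---|---|---|---|---|
| 1.0 | 0.350 | 0.765 | 0.827 | 0.864 |
| 0.9 | 0.315 | 0.662 | 0.717 | 0.772 |
| 0.8 | 0.280 | 0.540 | 0.575 | 0.648 |
| 0.5 | 0.175 | 0.163 | 0.133 | 0.201 |

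Only laboratory-only events are clearly at risk of being missed. If they are a fraction f of the total and are captured with probability c, then s = 1 − f(1 − c). With c = 0.5, s = 0.9 needs f = 0.2 (1 − 0.2 × 0.5 = 0.9), while s = 0.5 needs f = 1, meaning that every grade 3 or higher toxicity is silent. The bottom row is a bounding case, not an estimate.

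**Step 6: order timing.** Orders for doses 2 and 3 are written at a team meeting held before the injection day (section 9.7). The labs that bear on section 8.5.1.1 are marked on the injection day (Table 6). No passage states whether their results are available before the injection. The ±4-day allowance under Table 6 is for holidays or extenuating circumstances, so it does not settle the question.

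**The case against.** The strongest case against the point is that the plan captures events by other means. Section 6.2 requires all adverse events to be documented with onset and offset dates through Day 90. The section 7.1 interview asks about reactions already experienced, and section 8.5.1 continues monitoring for 30 days after the last injection. A symptomatic grade 3 event on Day 10 can therefore be recorded at Day 30 and counted. This stands. A reader might infer that transient toxicity escapes the rules altogether, or that any toxicity resolving within 30 days goes unmeasured; the documents do not support that for symptomatic or local events. Nor do they support the inference that the dose hold is defeated, for the reason in step 3.

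A second argument is that the sentence naming Days 44 and 74 only says where outside-center patients attend. It also covers 6, 9 and 12 months, when Table 6 marks no physical examination either, and laboratory testing could mean the immunology blood. This weakens the conflict: one cannot read 7.1 as firmly committing all patients to examinations on those days. It does not remove the ambiguity, because the later visits at least carry vital signs, weight and performance status, while Days 44 and 74 carry no clinical item.

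Third, the documents mention a detailed data and safety monitoring plan held by the monitoring committee, which may say more, and they report no significant adverse event in Phase I. Both are fair cautions on severity. Neither reconciles the text that sites will follow.

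**Conclusion.** The point holds as an inconsistency and a limited gap. The calendar and section 7.1 do not agree clearly on what is done at Days 44 and 74. For all three doses, the first scheduled safety check after the observation period comes about 30 days later. The exposed events are asymptomatic laboratory toxicities that arise and resolve between visits, and local reactions that have faded and must be graded from recall. The direction of any error is toward under-counting, which would make the stopping boundaries less likely to be reached.

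The size is unknown. The sensitivity table shows that the rule is not robust to missed events: under an assumed 20% loss, the chance of stopping at a true 35% rate falls from 0.864 to 0.648. It says nothing about how many events would be missed. A reader might go further and claim that a true 35% rate would appear as 18–28%. That requires an unsourced 50–80% detection rate for laboratory events, applied to all grade 3 or higher toxicity, and the documents do not support it.

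The change is worth making because it is cheap, improves ascertainment for two of the three doses, and serves the only early-stopping rule.

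**What to change.** 1. Reconcile Table 6 with section 7.1: mark adverse event assessment and injection-site examination at Days 44 and 74 for all patients, whichever site they attend. Keep section 7.6 pointing to the revised table.
2. Add CBC with differential and the chemistry panel to the blood already drawn at those two visits.
3. Separately, reconcile section 9.7, Table 6 and section 8.5.1.1 so that the text says when safety laboratory results are available relative to each injection. What the clinical rule should be is for the investigators to decide.

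The cost is minor: laboratory charges and some staff time at two visits that already take place. The limits should be stated openly. Dose 1 still has no interim visit. Day 74 follows the last dose, so it improves safety data and stopping counts but cannot inform any later injection.
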